Study endpoints	
The Primary Endpoint of this study is:
 
 • To assess the safety and tolerability of dantrolene sodium administered orally up to 100 mg b.i.d. (adults) and up to 2 mg/kg b.i.d. (pediatric patients, up to 50 kg) for 6 months with an optional extension phase up to 24 months in patients with Wolfram syndrome. • Safety will be assessed by adverse events (by type and severity) and changes in clinical laboratory testing (including liver function tests). • This will be assessed by monitoring of serum chemistry including liver function tests and ammonia. • Safety will be also assessed by complete physical exam (PE), vital signs (vs)/weight (wt) at each visit 
The Secondary Endpoints include:
 
 • Determine the effect of dantrolene sodium on remaining beta cell functions using a mixed-meal tolerance test and monitoring base-line C-peptide levels, blood glucose levels, proinsulin/C-peptide ratios, hemoglobin A1c levels, and urine glucose levels. • To determine the efficacy of dantrolene sodium on visual acuity (LogMar scores) • To determine the efficacy of dantrolene dosicum on visual functions using Visual Functioning Questionnaire – 25. • To evaluate the efficacy of dantrolene sodium on neurological functions using the Wolfram Unified Rating Scale (WURS) and standard neurological assessments.
Inclusion criteria	
Patients must meet all of the following criteria to be eligible for enrolment:
 
 1. The patient has a definitive diagnosis of Wolfram syndrome, as determined by the following: 
 a. Documented functionally relevant recessive mutations on both alleles of the WFS1 gene or dominant mutation on one allele of the WFS1 gene based on historical test results (if available) or from a qualified laboratory at screening. 2. The patient is at least 5 years of age (biological age) at the time of written informed consent. 3. The patient, patient's parent(s), or legally authorized guardian(s) must have voluntarily signed an Institutional Review Board/Independent Ethics Committee-approved

	
informed consent form after all relevant aspects of the study have been explained and discussed with the patient. The guardians' consent and patient's assent, as relevant, must be obtained.

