	
Up to 25 mg once daily for seven days as prescribed by the physician, then Up to 25 mg b.i.d. for seven days Up to 50 mg b.i.d. for seven days Up to 100 mg b.i.d.
 
Pediatric Patients (a patient with an age < 18 years) up to 50 kg Up to 0.5 mg/kg once daily for seven days as prescribed by the physician, then Up to 0.5 mg/kg b.i.d. for seven days Up to 1 mg/kg b.i.d. for seven days Up to 2 mg/kg b.i.d.
 
No dose changes if weight change is within $\pm 3\%$ of the original dosing weight.
 
Dantrolene sodium for oral use will be provided by the Washington University's clinical trials pharmacy

Study duration	The duration of this study will be approximately 9 months. For participants who continue in the optional extension phase, the duration of the study is up to 27 months.
Study methodology	
This is a single center, dose-escalation study designed to evaluate the safety, and tolerability of maximal dose level of dantrolene sodium administered orally over 6 months with an optional extension phase up to 24 months in patients with Wolfram syndrome.
 
The study will have 'x' periods as follows:
 
 Baseline and confirmatory screening (all patients): within 56 days prior to treatment. Dose maximization period (weeks 0-3 for each patient). Treatment period (weeks 1-) for all patients. Week 0 through week 3 (+/- 2 days): dose escalation up to the maximum recommended. Assessments for safety at months 1 (+/- 2 days), 2 (+/- 7 days), 4 (+/- 7 days), and 6 (+/- 7 days); and clinical examination, including ophthalmic, neurologic, endocrine, and laboratory assessments at months 0 and 6 (+/- 7 days). For participants who continue in the optional extension phase, additional assessments for safety at months 12 (+/- 7 days), 18 (+/- 7 days), and 24 (+/- 7 days); and additional clinical examinations, including ophthalmic, neurologic, endocrine, and laboratory assessments at months 12 (+/- 7 days), 18 (+/- 7 days) and 24 (+/- 7 days). Outcome measure evaluations (all patients): month 6 (+/- 7 days) after the last dantrolene sodium administration for participants who complete the study, month 24 (+/- 7 days) after the last dantrolene sodium administration for participants who complete the optional extension phase, and within 28 days (+/- 7 days) after the last dantrolene sodium

administration for patients who discontinue prior to the end of the study.

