Statistical Methodology	
The first aim of the statistical analysis will be to assess safety and tolerability of dantrolene sodium in this patient population. The analysis will be based on all enrolled patients and will not include any formal statistical tests. To evaluate safety, the number and percentage experiencing each adverse event will be tabulated and compared by treatment status. Adverse events will be summarized by severity and by category. Vital signs, and serum chemistries, hematology and urinalysis safety monitoring will be listed for each patient and abnormal values will be flagged. The maximum dose received by patients, duration of treatment and reasons for dose reductions or early withdrawal will be reported to assess tolerability of treatment.
 
The second aim of the statistical analysis will be to assess efficacy in terms of the secondary outcome measures of residual beta cell functions, visual acuity, and neurological function. Each variable will be quantified as a change from the baseline value. The trajectory of change for each variable will be assessed between baseline and 6-month assessments. For participants in the optional extension phase, the trajectory of change for each variable will be assessed between baseline, 6-month, 12-month, 18-month, and 24-month assessments..
 
As this is a rare disease and the trial involves only a small numbers of patients, statistical inferences will be based on estimation rather than hypothesis testing. Specifically a Bayesian approach to estimation will be used based on both non-informative and informative priors as appropriate. This type of approach has been endorsed for trials of rare diseases. Drop-outs may be replaced, such that an adequate number of evaluable patients complete the study.

Individual stopping criteria	
1. If a participant experiences more than a few but not more than 10 diarrhea stools in a single day while taking dantrolene sodium, a temporary withdrawal (48 h or longer) should be discussed with a PI. A patient with Wolfram syndrome tends to

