	
have diarrhea due to autonomic dysfunction. Thus, the temporary withdrawal is determined by the discretion of the PI. If a patient experiences more than 10 diarrhea stools in a single day, a temporary withdrawal (48 h or longer) should be immediately done. After the temporary withdrawal, a participant should use the previously tolerated dosing regimen.
 
2. If a participant experiences significant muscle weakness while taking dantrolene sodium, a participant should use the previously tolerated dosing regimen. Muscle weakness is examined at every study visit as part of the physical exam. Muscle weakness is assessed by the following methods.
 
 • Rise to stand from floor without using hands. If a participant cannot do this due to neurological dysfunction of Wolfram syndrome, the order in which we would like a participant to attempt is the following: From floor with hands, from a chair without using hands, from a chair with hands. • Hand grip strength using a hand dynamometer, left and right. 
If a participant cannot rise to stand with the method he/she used or a participant's total hand grip strength (sum of right- and left-hand grip strength) is decreased by more than 20% with the current dosing regimen, a patient should use the previously tolerated dosing regimen.
 
Two failures in either of these two steps would constitute stopping the drug permanently.
 
3. ALT or AST >8xUpper Limits of Normal (ULN) 4. ALT or AST >5xULN for more than 2 weeks 5. ALT or AST >3xULN and (serum total bilirubin >2xULN or international normalized ratio >1.5) 6. ALT or AST >3xULN with the appearance of fatigue, nausea, vomiting, right upper quadrant pain or tenderness, fever, rash, and/or eosinophilia (>5%)

Study stopping criteria	We define the study stopping criteria based on established adverse event criteria, the National Cancer Institute (NCI) Common Terminology Criteria for Adverse Events (CTCAE), Version 4. The study may need to be stopped if ≥2 patients on drug develop the same CTCAE Grade 3 or if 1 patient develops a CTCAE Grade 4 or higher.

FIGURE: CLINICAL TRIAL DIAGRAM

For participants who continue in the optional extension phase

**Study Visits 10,
11, and 12
Month 12, 18,
and 24**

Assessment of Clinical Outcome Measures

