Discontinue study med or placebo; Complete PE, VS/Wt, all safety labs and evaluative labs: liver enzyme testing (ALT, AST, alkaline phosphatase, bilirubin), Eval labs: blood glucose levels, CBC with differential, comprehensive metabolic panel, proinsulin, C-peptide, HbA1C, myelin basic protein and MANF levels (ELISA), osm, phos, Am, UA(micro/macro, glucose); ECG, beta cell functions, neurological and ophthalmology exam, visual functioning questions, QOL questions.

Final Follow up

Safety labs, AE monitoring, complete PE, VS/Wt

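### Grip strength and rise-to-stand are tested at every visit because weakness on drug is foreseen, yet no planned safety or efficacy analysis uses them

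*Combined protocol and SAP*

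**What the plan says.** All references are to the combined protocol and SAP.

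- **Individual stopping criteria, item 2.** Weakness is treated as an event that may occur on drug and calls for action: "If a participant experiences significant muscle weakness while taking dantrolene sodium, a participant should use the previously tolerated dosing regimen". Two tests are used, rise-to-stand and total grip (right plus left). On timing: "Muscle weakness is examined at every study visit as part of the physical exam". Action follows if the patient can no longer rise by the method used before, or if total grip falls by more than 20%. Repeated failure leads to permanent stopping.
- **Study endpoints.** The physical exam at each visit is part of the primary safety assessment. A secondary endpoint is: "To evaluate the efficacy of dantrolene sodium on neurological functions using the Wolfram Unified Rating Scale (WURS) and standard neurological assessments".
- **Statistical Methodology, first aim.** The safety summaries cover adverse events, vital signs, chemistry, hematology, urinalysis, maximum dose, treatment duration, and reasons for dose reduction or withdrawal. Physical exam findings, grip and rise-to-stand are not named.
- **Statistical Methodology, second aim.** Efficacy covers the "secondary outcome measures of residual beta cell functions, visual acuity, and neurological function". The method is: "Each variable will be quantified as a change from the baseline value". Further, "statistical inferences will be based on estimation rather than hypothesis testing". Strength and on-drug or off-drug status are not mentioned.
- **Clinical trial diagram, Final Follow up.** The content is "Safety labs, AE monitoring, complete PE, VS/Wt". Neither the WURS nor a neurological examination is listed.

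**The concern.** Two things are at stake.

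The first is the primary question. Grip is the one numerical measure the protocol has of a drug effect that it foresees. If grip is used to trigger dosing decisions but never summarised, a moderate loss shared by many patients can leave no trace in the safety report.

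The second is the reading of neurological change. The WURS is analysed as a change from a pre-drug baseline, and no concurrent control is described that would subtract an effect of the drug on muscle. If strength affects the score, weakness caused by the drug is counted as neurological change. Patients who stop early are evaluated after their last dose, when such weakness may have eased. The change scores may then mix two states, and membership of the off-drug group may itself depend on weakness.

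**Working it through.** **Sample size.** This is the plan's only figure near this point, and the point does not rest on it. Enrolment is 50 with 10% drop-out: 50 × 0.90 = 45, against 46 stated. By group, 25 × 0.90 = 22.5, rounded up to 23, and 2 × 23 = 46. The figure is reproduced to within one patient. About 50 × 0.10 = 5 patients would be evaluated after stopping early.

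**What the safety tables can miss.** I take the pre-dose value as the reference for the grip rule; the rule does not state one. If pre-dose total grip is 100%, any value from 80% upwards is a fall of no more than 20% and does not meet the grip trigger. Failing rise-to-stand triggers action whatever the grip value. A patient who still rises as before with grip at 80% therefore has no dose reduction to report, and has an adverse event only if someone records one. The 20% is a ceiling under the grip rule, not an expected loss.

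**When completers are evaluated.** The texts conflict:

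1. The list of periods in Study methodology places the evaluation at month 6 after the last administration (month 24 for the extension).
2. Later in the same section, all patients are evaluated at month 6.
3. The diagram box for months 12, 18 and 24 opens with discontinuing study medication, although months 12 and 18 fall within continuing treatment.

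The stated durations allow a check, at 30.4 days per month. Screening is up to 56 / 30.4 = 1.84 months and follow-up is 28 / 30.4 = 0.92 months.

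| Reading | Sum (months) | Total | Stated |
|---|---|---|---|
| Evaluation at end of 6 months' dosing | 1.84 + 6 + 0.92 | 8.8 | 9 |
| Evaluation 6 months after last dose | 1.84 + 6 + 6 + 0.92 | 14.8 | 9 |
| Evaluation at end of 24 months' dosing | 1.84 + 24 + 0.92 | 26.8 | 27 |

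Evaluation at the end of dosing fits both stated durations. Early discontinuers, by contrast, are evaluated within 28 (± 7) days after the last dose, so off drug.

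**Direction.** Weakness can only push a strength-dependent score toward worsening. It can imitate progression or offset a benefit. It cannot produce an improvement, though it could understate one.

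**Size (illustration on assumed inputs).** Let a fraction f of patients have a drug-caused WURS worsening of d standard deviations (SD) of the change score. The mean then shifts by f × d.

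- Low end: 0.10 × 0.25 = 0.025 SD.
- High end: 0.50 × 1.0 = 0.50 SD.
- Yardstick: the 95% half-width of a mean change is t(0.975, n − 1) / √n, which is 0.297 SD at n = 46 and 0.432 SD at n = 23.
- Relative to n = 46: 0.025 / 0.297 = 8% and 0.50 / 0.297 = 168%.

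The shift could be negligible or could dominate. The documents do not allow one to say which, and the planned tables would not show it.

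**The case against.** The sponsor could fairly say that weakness is already covered. The tests belong to the physical exam, which is a named safety assessment; adverse events are tabulated; and reasons for dose reduction are reported. That stands for weakness that triggers action, so a reader who infers that the strength data serve dosing alone goes too far. What is missing is a numerical summary by visit, and the losses below the threshold are missing with it.

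Three stronger readings are tempting, and the documents do not support them.

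- **That no WURS change can be read as an effect on the disease.** On this mechanism an improvement is not undermined. The documents give no WURS items, so its dependence on strength is an assumption. The broader limit on attribution is the design: "This is a single center, dose-escalation study designed to evaluate the safety, and tolerability of maximal dose level", with no control arm described.
- **That grip and rise-to-stand could separate drug from disease.** The stopping criteria themselves recognise that Wolfram syndrome can limit rising from the floor. Neurologic examination in the main phase is listed at months 0 and 6, and the WURS is not listed at final follow-up. Change from pre-dose to month 1, or from month 6 to follow-up, therefore sizes a grip effect and not a WURS effect. Patients who enter the extension have no off-drug visit after month 6.
- **That completers are certainly on drug at month 6.** The durations make evaluation at the end of dosing likely, but the text conflicts.

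The sponsor could add that pooling is nowhere stated: evaluable patients are those who complete, and drop-outs may be replaced. This is fair. The plan does not rule pooling out either.

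**Conclusion.** The point holds as a gap in the analysis plan. A foreseen drug effect is measured at every visit and summarised nowhere, and a grip loss of up to 20% can go unreported in a trial whose primary question is safety. For the WURS the consequence is one-sided and conditional: a worsening or a null result would be ambiguous if grip has also fallen, and a benefit could be hidden. Its size cannot be fixed from the documents; the 8% to 168% range rests on assumed values of f and d.

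The conclusion assumes that grip and rise-to-stand are recorded at baseline and at final follow-up. This follows from the every-visit statement and from the complete physical exam listed at both. The WURS is a secondary, estimation-only endpoint in a Phase 1b trial, so this is an inexpensive improvement and not a flaw that undermines the trial.

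**What to change.** In Statistical Methodology:

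1. Add change from pre-dose in total grip strength, and change in rise-to-stand method, as safety outcomes at each visit including the final follow-up. Early on-drug change and any recovery of grip off drug can then be seen. Confirm that both tests are recorded before the first dose and at final follow-up.
2. Report WURS change by on-drug or off-drug status at evaluation, beside the same patient's grip change, and do not pool the two states in the main estimate.
3. State that WURS worsening, or no change, accompanied by grip loss will not be attributed to disease progression or lack of benefit alone.

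Do not add a rule that discounts every WURS change when grip recovers off drug. The WURS is not listed for repetition at that visit, and such a rule would also discard improvements.

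In Study methodology and the clinical trial diagram, reconcile the statements on when completers and extension participants are evaluated relative to their last dose.

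The cost is SAP wording and a few tables from data the protocol already collects. No dosing or stopping rule is touched. The neurological conclusion becomes somewhat more cautious.
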